**Table 1. Summary of Study Procedures**

Time points	ToPIC participants	TTAU participants	Outcome	Compensation
Pregnant Patient Participants:				
Baseline <20 weeks gestation	
 
• Urine cotinine
 
• EACO
 
• ACOG tobacco use screen
 
	
 
• Urine cotinine
 
• EACO
 
• ACOG tobacco use
 
	Eligibility screen for tobacco	\$10
Monthly through end of pregnancy at regularly scheduled prenatal visits	
 
• CTTS tobacco treatment education support, including
 
• Individualized treatment plan (baseline)
 
• 5As
 
• Motivational Interviewing
 
• Navigation to resources
 
	
 
• 5As, as per usual
 
		
28-34 weeks gestation	
 
• Urine cotinine
 
• EACO
 
• TUQ
 
	
 
• Urine cotinine
 
• EACO
 
• TUQ
 
	Tobacco cessation or reduction	\$10
Postpartum 2-8 weeks after delivery	
 
• Urine cotinine
 
• EACO
 
• TUQ
 
	
 
• Urine cotinine
 
• EACO
 
• TUQ
 
	Tobacco cessation or reduction	\$20
Postpartum 12-18 weeks after delivery	
 
• Urine cotinine
 
• EACO
 
• TUQ
 
	
 
• Urine cotinine
 
• EACO
 
• TUQ
 
	Tobacco cessation or reduction	\$20

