### Statistical Analysis Plan

Analysis and estimated power: **Primary outcome:** The primary outcome is smoking cessation in the third trimester, defined as urine cotinine level of <100 ng/mL. **Secondary outcomes** include: self-reported number of cigarettes smoked/day, smoking cessation after delivery, infant birth weight, gestational age at delivery, health care utilization outside of scheduled normal prenatal and infant well-child visits. Two-factor mixed models with group by time interactions will be employed to analyze longitudinal continuous data collected over the course of the trial. Significant main and interaction effects will be explored further using Tukey post-hoc tests. Generalized estimating equation (GEE) modeling will be used to test for significant differences between groups and across time for categorical and dichotomous outcomes; these models will also consider possible group by time interactions. Post-hoc analysis of significant main or interaction effects in the GEE models will be accomplished using contrasts. Demographic and personal factors (e.g., maternal age, gestational age at enrollment) may be included as covariates if linked to outcomes in bivariate analysis. We **hypothesize** that compared with the TTAU group, the ToPIC group will have higher tobacco cessation rates, fewer infants born preterm, and fewer ill child health care visits. While we will assess group differences over time

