in this way, the emphasis on the analysis will be the detection of average differences between the groups, so that we may use this to estimate effect sizes for a larger study in the future. With 60 participants per group and an alpha level of .05, the power of the repeated measures mixed model F test will have at least 90% power to detect a medium effect in the context of group differences, time differences, or a group by time interaction. A medium effect is such that the ratio of the standard deviation of the group means to the standard deviation of the observations within the populations is at least 0.25. While an effect size driven algorithm for estimating the power associated with GEE models has not been developed, logistic regression is considered as a similar technique. With 120 participants and an alpha level of .05, the power of logistic regression to detect an odds ratio as small as 2.3 will be at least 91%. One way to attain an odds ratio of this magnitude would be if the percent of participants in each group with a particular outcome were 50% versus 30%. The power associated with the corresponding GEE model (and extension of logistic regression to the longitudinal application) is expected to be at least as large, given the additional time points included. Power estimates were obtained using nQuery Advisor, v. 6.02 (Elashoff, J. 1995-2005. nQuery Advisor, Statistical Solutions. Saugus, MA).

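### The primary outcome is cessation at one third-trimester visit, but the SAP names no contrast at that visit as primary and puts its emphasis on an average group difference that may include secondary visits

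*Combined protocol and SAP*

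**What the plan says.** All of this is in the Statistical Analysis Plan section of the combined document, except for Table 1.

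- Primary outcome: "The primary outcome is smoking cessation in the third trimester, defined as urine cotinine level of <100 ng/mL".
- Among the secondary outcomes: "smoking cessation after delivery".
- Table 1 schedules urine cotinine at baseline (before 20 weeks), at "28-34 weeks gestation", and at two postpartum visits (2-8 and 12-18 weeks). The 28-34 week visit is the only follow-up cotinine test before delivery, so it alone can supply the primary outcome.
- Dichotomous outcomes are to be analysed by a GEE that tests group and time and considers their interaction. Contrasts have one role: "Post-hoc analysis of significant main or interaction effects in the GEE models will be accomplished using contrasts".
- The emphasis is then set: "the emphasis on the analysis will be the detection of average differences between the groups". It is placed against the longitudinal comparison ("While we will assess group differences over time"), and a purpose is attached to it: "so that we may use this to estimate effect sizes for a larger study in the future".
- The power of the GEE, compared with an ordinary logistic regression, "is expected to be at least as large, given the additional time points included".

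No sentence ties the primary test or estimate to the 28-34 week visit. None says which visits enter the GEE.

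**The concern.** Defining an outcome at one visit does not settle which parameter of a multi-visit model is the primary result. Two candidates remain: the group contrast at 28-34 weeks, and a group effect taken over several visits. The second would mix the primary visit with visits whose outcome the plan itself calls secondary.

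The choice matters because the plan intends to carry its effect size into a larger study. If the intervention effect changes after delivery, the two candidates differ, and the number carried forward may not describe the declared primary outcome. A constant effect cannot be presumed: the plan allows for a group-by-time interaction, and Box 2 includes postpartum relapse prevention in the counselling.

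There is a smaller, procedural consequence. If contrasts are examined only after a significant main or interaction effect, the comparison that matches the primary outcome might not be examined in some trials.

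**Working it through.** **Inputs from the documents.** 60 per group; alpha 0.05 (sidedness not stated, two-sided assumed); illustrative rates 50% versus 30%; one third-trimester and two postpartum cotinine visits.

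**Assumed, because the documents do not give them.** Visit-specific rates, within-person correlation, no dropout, no clinic clustering.

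**1. The plan's own power figure.** The plan states at least 91% for an odds ratio of 2.3 with 120 participants and illustrates it by 50% versus 30%. The odds ratio is (0.5/0.5)/(0.3/0.7) = 2.33. For a two-group comparison at one visit:

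- SE under the null = √(2 × 0.4 × 0.6/60) = 0.0894
- SE under the alternative = √((0.25 + 0.21)/60) = 0.0876
- z = (0.20 − 1.96 × 0.0894)/0.0876 = 0.28, so power = 61% (73% one-sided)

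The 91% is not reproduced. That is a separate matter; what counts here is that the 28-34 week contrast has about 61%.

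**2. Which reading the power text fits.** For continuous outcomes the plan claims at least 90% power at f = 0.25. At a single visit λ = 0.25² × 120 = 7.5, and the F test on 1 and 118 degrees of freedom has 77.5% power. Averaged over three visits, λ = 7.5 × 3/(1 + 2ρ), which gives 96%, 91% and 86% at ρ = 0.3, 0.5 and 0.7. The power text therefore sits more easily with a comparison that uses several visits. This is indirect evidence, and it concerns the continuous outcomes.

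**3. Third-trimester versus averaged odds ratio.** Equal weights on the logit scale, averaged OR = exp{mean over visits of [logit(p ToPIC) − logit(p TTAU)]}. The rates are for 28-34 weeks, then the two postpartum visits.

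| Assumed pattern | ToPIC % | TTAU % | Mean logits | OR at 28-34 weeks | Averaged OR |
|---|---|---|---|---|---|
| Constant | 50/50/50 | 30/30/30 | 0; −0.847 | 2.33 | 2.33 |
| Mild waning | 50/45/40 | 30/28/26 | −0.202; −0.946 | 2.33 | 2.10 |
| Steeper waning | 50/35/30 | 30/27/25 | −0.489; −0.980 | 2.33 | 1.63 |
| Postpartum only | 30/40/45 | 30/25/25 | −0.484; −1.015 | 1.00 | 1.70 |

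These are population values with equal weights. A GEE with another working correlation may weight the visits differently.

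**4. The visit list matters too.** If baseline also enters, with equal rates in both groups and a constant effect afterwards, the equal-weight average falls to 2.33^(3/4) = 1.89.

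**5. Power of the two candidates.** Simulation: binary outcomes from a thresholded multivariate normal, latent correlation 0.5 to 0.8, 60 per group, robust tests.

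| Pattern | 28-34 week contrast | Three-visit average |
|---|---|---|
| Constant | 61-62% | 75-86% |
| Mild waning | 61-62% | 62-76% |
| Steeper waning | 61-62% | 31-45% |

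The ranges for the average cover equal-weight and exchangeable-GEE versions. A closed-form check for the constant case, with a correlation of 0.5 between the binary outcomes: SE = √(0.46 × (2/3)/60) = 0.0715, z = 0.20/0.0715 − 1.96 = 0.84, power 80%.

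**6. The follow-up rule as written.** Time is a main effect in these models, so a significant time effect also opens contrasts. With the three follow-up visits only, the share of simulated trials in which the 28-34 week contrast is significant but none of group, time or interaction is:

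- mild waning: 3.6%, 4.2%, 4.5% at latent correlations 0.5, 0.7, 0.8
- steeper waning: 6.2%, 4.2%, 3.1%

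If baseline enters, with an assumed 10% below the cut-off, time is significant in essentially every trial and the share is about nil.

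**The case against.** The best reply is that pooling is read into the text. The emphasis sentence follows hypotheses that include preterm birth, which has no repeated visits. For such an outcome an average difference cannot mean an average over visits, so the phrase may simply mean a difference in group means or rates. The remark about additional time points concerns power and does not define what is estimated. The binary power illustration uses one proportion per group. The study is also a pilot whose own text concedes limited power and cannot fully separate intervention from clinic; naming a contrast does not change that.

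Much of this stands. A reader might infer that the SAP replaces its primary outcome with a pooled one, or withholds the third-trimester comparison. The documents say neither. A reader might also count only the group and interaction terms as opening contrasts and find a larger loss than in step 6; the SAP's wording covers main effects generally, and time is one. Finally, a reader might turn the odds ratios into per-arm sample sizes for the larger study. That study is described, in the text after Box 2, as group randomised with several clinics per treatment, so sizes for individual randomisation would not apply.

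What the reply does not remove is the omission. On either reading of the average, no primary contrast is named and the visits are not listed. The pilot's purpose makes it more important, not less, to know which effect is carried forward.

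**Conclusion.** The point holds in a limited form and should be corrected. It is certain that the SAP leaves the primary contrast and the GEE visits unspecified. That the emphasised estimate is visit-averaged is plausible but inferred, and confidence in that part is medium.

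If it is averaged, it need not equal the effect on the declared primary outcome: 2.10 or 1.63 against 2.33 under the two waning patterns, 1.70 against 1.0 under the postpartum-only pattern, and no gap if the effect is constant. The documents give no visit-specific rates, so the true direction and size of any gap are unknown. The follow-up rule is a minor part of the problem, at roughly 3 to 6% of trials under the assumed waning patterns with baseline excluded.

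**What to change.** Amend the Statistical Analysis Plan to state that:

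- the primary analysis is the ToPIC versus TTAU contrast in cessation (urine cotinine below 100 ng/mL) at the 28-34 week visit, from the GEE or a single-visit model, reported as a risk difference and odds ratio with 95% confidence intervals, whether or not the group or interaction term is significant;
- the postpartum contrasts and the visit-averaged difference are secondary;
- the visits entering the GEE are listed, including whether baseline is one of them;
- power is restated for the primary contrast: about 61%, two-sided, for 50% versus 30% with 60 per group, before clustering or dropout.

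No new data are needed. The real cost is power. Under a constant 50% versus 30%, the single-visit contrast has about 61% against about 75 to 86% for the three-visit average, a loss of 14 to 25 points. That is a reason to keep the average as a reported secondary result, not to leave the primary one unnamed.

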## BOX 2. Typical Counseling Session with a CTTS for Pregnant Women

- Assessment of tobacco use and tobacco use history using an evidence-based tool
- Motivational and practical counseling based on assessment of readiness, including providing education on the maternal and fetal health impacts of smoking
- Provide strong advice to quit as soon as possible
- Exploration of the pros and cons of tobacco use/quitting (decisional balance) and triggers/cues to smoke, including partner smoking and potential engagement in treatment
- Collaboratively developing a tailored treatment plan, which may include but is not limited to incentives, and trigger management strategies, such as stress management or partner support
- Setting a quit date with close follow up
- Discussion relapse prevention strategies during the perinatal and postpartum periods

Our target sample size is 60 participants in each the intervention and control group, for a total of 120 pregnant participants for this pilot project. Additionally, 12 clinic staff and providers will provide quantitative and qualitative data for a mixed-method, multi-stakeholder process evaluation of intervention training and delivery. Due to our limitation of only two participating clinics, we acknowledge that it will not be possible to fully distinguish the effects of the intervention from differences between the two clinic populations. A future larger study of this intervention will include a true group randomized trial, with multiple clinics per treatment, so that the effect of nesting of patients within clinics within treatment will be estimable. In light of this limitation, we will use sample demographic characteristics as covariates in the repeated measures mixed modeling; we acknowledge that the group effects are still likely to be somewhat inflated in this analysis, given the expected artificially small errors due to correlations among patients who visit the same clinic and who may see the same provider. Although we will have limited power, the results from this pilot proof-of-concept study will provide preliminary data to support a highly competitive NIH Health Care Systems Research Pragmatic Trial application.

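### The stated power of at least 91% for an odds ratio of 2.3 is wrong: 50% versus 30% at one time point with 60 women per group has about 61–63%, and neither power figure allows for clinic variation

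*Combined protocol and SAP*

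**What the plan says.** The protocol's sample-size paragraph (after Box 2) sets the numbers: "Our target sample size is 60 participants in each the intervention and control group", 120 in all. The Statistical Analysis Plan defines the endpoint: "The primary outcome is smoking cessation in the third trimester, defined as urine cotinine level of <100 ng/mL". Binary outcomes are to be analysed by GEE, with tests of group, time and their interaction.

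The plan has no power method for GEE, so it uses logistic regression as a stand-in. It says that, with 120 participants and alpha .05, "the power of logistic regression to detect an odds ratio as small as 2.3 will be at least 91"%. It adds that such an odds ratio would arise "if the percent of participants in each group with a particular outcome were 50% versus 30"%. Power for the GEE model "is expected to be at least as large, given the additional time points included". For continuous outcomes it claims at least 90% power for a medium effect (f = 0.25) on group, time or interaction.

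The sample-size paragraph is more cautious. It begins its caveat with "Due to our limitation of only two participating clinics", grants that intervention and clinic effects cannot be fully separated and that errors will come out too small, and ends: "Although we will have limited power, the results from this pilot proof-of-concept study will provide preliminary data".

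**The concern.** A 20-point difference between two groups of 60 is not normally detectable with power above 90%, so the 91% looked too high on sight. It is the only numerical power statement that covers the binary primary outcome. A reader who trusts it would take a null pilot result as fair evidence against an effect as large as 50% versus 30%. If true power is near 62%, the design misses that effect nearly four times in ten, before any clinic variation or dropout. The SAP also intends to carry the observed effect size into a larger study, so a misread pilot has consequences beyond itself.

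A second, lesser point is that the protocol warns of clinic correlation and limited power, yet nothing of that warning enters either power figure.

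**Working it through.** **Inputs.** n = 60 per group (protocol, after Box 2). Alpha .05 and 50% versus 30% (SAP). The odds ratio of the example is (0.5/0.5)/(0.3/0.7) = 2.33. Assumed, because not stated: two-sided testing, complete data, independent women.

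**The plan's own figure, single time point.**
- SE under the null: sqrt(2 × 0.4 × 0.6/60) = 0.0894
- SE under the alternative: sqrt((0.25 + 0.21)/60) = 0.0876
- Pooled power: Φ((0.2 − 1.96 × 0.0894)/0.0876) = 61.1%
- Unpooled power: Φ(0.2/0.0876 − 1.96) = 62.7%
- Exact enumeration, Pearson chi-square: 61.8%
- n for 91% (pooled): (1.96 × sqrt(0.48) + 1.341 × sqrt(0.46))²/0.2² = 128.5, so 129 per group

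**Attempts to recover 91%.**
- One-sided alpha .05: 73–74%.
- Reading 120 as the number per arm: 89.0% two-sided (pooled). It passes 91% only if testing is also one-sided (93.9%), and 120 per arm contradicts the stated total.
- Other control rates at an odds ratio of exactly 2.3: at most 63.5% (exact), near 39.5% versus 60%. The 50% versus 30% example is therefore not the cause.
- Larger effects: 60 per group reach 91% only from an odds ratio of about 3.4, for example 30% versus 59%.

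A logistic power formula for a one-SD change in a continuous covariate, with event rate 30% and N = 120, gives 90.8% at an odds ratio of 2.3 and 91.2% at 2.33. That may be the origin, but this is inference. Such a formula does not apply to a two-group comparison.

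**Extra time points.** Table 1 has three follow-ups: 28–34 weeks' gestation, 2–8 weeks postpartum, and "Postpartum 12-18 weeks after delivery". Only the first can supply the third-trimester outcome. For an average over all three, assume 50% versus 30% at each and a common within-woman correlation ρ. The variance is multiplied by (1 + 2ρ)/3:

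| ρ (assumed) | Pooled | Unpooled |
|---|---|---|
| 0.3 | 87.0% | 87.9% |
| 0.5 | 78.7% | 79.9% |
| 0.7 | 70.9% | 72.4% |

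Simulation of the GEE group test with robust standard errors gave 86.8%, 78.6% and 71.1%. Power reaches 91% only at ρ of about 0.20 (pooled) to 0.22 (unpooled) or less.

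**The 90% for the mixed model.** For group differences over K time points, the noncentrality is 0.0625 × 120 × K/(1 + (K − 1)ρ) on 1 and 118 df. One time point gives 77.5%. The 90% holds up to ρ of about 0.55 with K = 3 or 0.60 with K = 4. For time or interaction effects, with noncentrality 0.0625 × 120 × K/(1 − ρ), power is at least 99% for K = 3 and any non-negative ρ under compound symmetry. The 90% is therefore not shown to be wrong, but for group differences it rests on a correlation that is not given.

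**Clinic variation.** With one clinic per arm there are no between-clinic degrees of freedom, so clinic variance cannot be estimated. For illustration, the 95% half-width for the single-time-point risk difference is 1.96 × 0.0876 × sqrt(1 + 59 × ICC). The ICC values are assumptions:

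| ICC | 0 | 0.001 | 0.01 | 0.02 | 0.05 |
|---|---|---|---|---|---|
| Half-width (points) | 17.2 | 17.7 | 21.6 | 25.3 | 34.1 |

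**The case against.** The best defence has four parts.

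- **Sidedness.** The SAP gives only alpha .05, and its hypothesis is directional. This is fair: two-sided testing is an assumption and must be labelled. One-sided, the three-visit average keeps 91% up to ρ of about 0.36 (pooled; 92.6% at 0.3). The single time point still reaches only 73–74%.
- **Target of the figure.** The SAP does not tie the 91% to third-trimester cessation, and it says its emphasis is on average group differences. For that average the shortfall is smaller (about 71–88%). But the sentence is about logistic regression on 120 women, before any gain from repeated measures is claimed, and as such it is wrong.
- **Disclosure.** The protocol openly reports the clinic confounding, the understated errors and the limited power. That stands, and the clinic point is secondary for that reason. A general admission of limited power does not correct a specific 91%, however; it contradicts it.
- **Pilot status.** The aim is preliminary data, and the documents do not derive 60 per group from the 91%. This means the sample size need not change. It does not make the number right.

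It is also fair to say that 61–63% is itself favourable, since it assumes no missing third-trimester data. An assumed loss of 10–30% lowers the pooled figure to about 57–46%.

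**Conclusion.** The concern holds. The 91% overstates power by about 30 percentage points (91 − 61 = 30; 91 − 63 = 28) for the effect the plan itself names, at a single time point such as the primary outcome. The conclusion rests on 60 independent women per group with complete data and two-sided alpha .05; one-sided testing reduces the gap but does not close it. The claim that GEE power is at least as large fails for the primary outcome. For the follow-up average it is supported only at a low within-woman correlation that the plan never states. The absence of any allowance for clinic variation in both power figures is real but secondary: it is disclosed, and rewording cannot remove it.

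**What to change.** 1. Withdraw the 91%. State about 61–63% for 50% versus 30% at a single time point, conditional on two-sided testing, independent women and complete third-trimester data. If power for the follow-up average is wanted, give it separately with its assumed within-woman correlation (about 71–88% for 0.7 down to 0.3).
2. State the within-woman correlation and number of time points behind the 90% for group differences. Say that neither figure allows for clinic variation, and bring the power paragraph into line with the protocol's statement of limited power.
3. Report group differences mainly as estimates with intervals. Optionally, for single-time-point contrasts, show beside the naive 95% interval one widened by sqrt(1 + (m − 1) × ICC), with m women per clinic, over a pre-stated assumed range such as 0.001–0.05. This does not remove confounding by clinic and is not suited to change-from-baseline or group-by-time contrasts.
4. A minor wording point: the Usual Care and Intervention paragraphs speak of women being randomized, while Study Design, Aim 1 and the sample-size paragraph describe a comparison of two clinics. Reconcile them.

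The cost is a corrected power paragraph and a few lines of SAP text. The plan will show a less favourable power figure and, if item 3's option is taken, wider intervals. No further participants or clinics are needed.

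### GEE power is not unconditionally at least as large as that of the single comparison: the postpartum visits add none for the third-trimester primary outcome, and help a pooled effect only if enough of it persists

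*Combined protocol and SAP*

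**What the plan says.** The Statistical Analysis Plan fixes the primary endpoint at one time: "The primary outcome is smoking cessation in the third trimester", judged by urine cotinine. Table 1 places that measurement at 28-34 weeks. It has two further follow-up cotinine visits, at 2-8 and 12-18 weeks after delivery. Cessation after delivery is listed separately as a secondary outcome. Table 1 schedules the CTTS counselling "Monthly through end of pregnancy at regularly scheduled prenatal visits".

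For dichotomous outcomes the plan uses GEE and will consider group-by-time terms. It says that a GEE power algorithm based on effect size is not available and turns to logistic regression instead. "With 120 participants and an alpha level of .05", it says, the power to "detect an odds ratio as small as 2.3 will be at least 91"%. It illustrates this odds ratio by supposing that "the percent of participants in each group with a particular outcome were 50% versus 30"%. GEE power then "is expected to be at least as large, given the additional time points included". The same section says that the analysis will emphasise average differences between the groups.

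The plan does not state which visits or which contrast the GEE test uses, nor a within-woman correlation, a postpartum effect or a dropout rate.

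**The concern.** The only reason given for GEE power being no lower is the number of time points. More measurements per woman help only if they bear on the quantity being tested. For a difference defined at 28-34 weeks, measurements after delivery do not, so long as the 28-34 week values are complete. For a difference averaged over visits they do, but if the effect weakens after delivery the average shrinks, and this can outweigh the gain in precision. Both added visits come after scheduled counselling ends, so persistence cannot be taken for granted.

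At stake is what the sponsor believes about the study. The text presents 91% as a level that the GEE should meet or exceed, for an analysis that includes the primary outcome. The pilot is meant to supply effect sizes for a larger trial, so the same reasoning could carry over into that trial's sample size.

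**Working it through.** **Inputs from the documents.** 60 women per group (section after Box 2: "Our target sample size is 60 participants in each the intervention and control group"); alpha .05; 50% v 30%; one primary visit and two postpartum visits (Table 1).

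**Assumptions.** Two-sided test, since sidedness is not stated; exchangeable within-woman correlation ρ of 0.3, 0.5 or 0.7; control rate 30% at every visit unless noted; share f of the third-trimester effect kept at both postpartum visits; no dropout; no clinic clustering.

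**1. The plan's own figure.** 50% v 30% is an odds ratio of (0.5/0.5)/(0.3/0.7) = 2.33. The two-group comparison at 28-34 weeks gives:
- Unpooled variance: SE = √[(0.25 + 0.21)/60] = 0.0876; power = Φ(0.20/0.0876 − 1.96) = Φ(0.324) = 62.7%.
- Pooled variance under the null: SE₀ = √(2 × 0.24/60) = 0.0894; power = Φ[(0.20 − 1.96 × 0.0894)/0.0876] = 61.1%.
- Wald test on the log odds ratio: SE = √(1/30 + 1/30 + 1/18 + 1/42) = 0.382; power = Φ(0.847/0.382 − 1.96) = 60.2%.

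None is near 91%. A formula for logistic regression on one normally distributed covariate (odds ratio 2.3 per standard deviation, event rate 30% at the mean, N = 120) gives 90.8%. That matches the stated figure but is not a two-group comparison.

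**2. Third-trimester contrast from the GEE.** With group, time and group-by-time terms and complete data, the 28-34 week contrast depends only on the 28-34 week proportions. Simulated logistic GEE with 500 runs per setting agrees: at ρ = 0.5 with a sustained effect, the rejection rate was 62.2% for the GEE contrast and 62.2% for the single-visit logistic test. The two rates were also identical in each of the six other settings run, which varied ρ and f.

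**3. Effect averaged over three visits.** With T = 3 and n = 60, d̄ is the mean of the visit differences, and

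Var = Σ over arms of [1/(nT²)] Σⱼₖ ρⱼₖ √(pⱼqⱼpₖqₖ), with ρⱼⱼ = 1; power = Φ(d̄/SE − 1.96).

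At ρ = 0.5:
- f = 1: d̄ = 0.20; Var = 0.007667 × (1 + 2 × 0.5)/3 = 0.005111; SE = 0.0715; Φ(2.798 − 1.96) = 79.9%.
- f = 0.75 (50/45/45% v 30%): d̄ = 0.1667; SE = 0.0714; Φ(2.335 − 1.96) = 64.6%.
- f = 0.5 (50/40/40% v 30%): d̄ = 0.1333; SE = 0.0710; Φ(1.879 − 1.96) = 46.8%.

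| Postpartum effect kept | ρ = 0.3 | ρ = 0.5 | ρ = 0.7 |
|---|---|---|---|
| All | 88% | 80% | 72% |
| 75% | 74% | 65% | 57% |
| Half | 56% | 47% | 40% |
| None | 19% | 16% | 14% |
| One visit only | 63% | 63% | 63% |

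**4. Break-even.** If the small change in variance is ignored, pooled power equals single-visit power when (1 + 2f)/3 = √[(1 + 2ρ)/3]. This gives f = 0.595, 0.725 and 0.842. Solved with the full variance, f = 0.59, 0.72 and 0.84 at ρ = 0.3, 0.5 and 0.7.

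**5. When a sustained effect reaches 91%.** This needs d̄/SE = 1.96 + 1.341 = 3.301, so Var = (0.20/3.301)² = 0.00367. Then (1 + 2ρ)/3 = 0.00367/0.007667 = 0.479, and ρ is about 0.22. At ρ = 0.2 power is 91.7%; at 0.3 it is 87.9%.

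**6. Sensitivity to the control rate.** If both arms relapse but the 20-point gap holds (50/40/40% v 30/20/20%), power is 91%, 83% and 76%. With 50/40/35% v 30/25/25% it is 68%, 58% and 50%.

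**The case against.** The strongest defence is that the sentence may not be about the primary outcome. Its illustration refers to an unspecified outcome, and the section says the emphasis is on average group differences. For that quantity a lasting effect does raise power, from 63% to between 72% and 88% in the table. Box 2 includes discussion of postpartum relapse prevention, so persistence is intended. The wording is also an expectation, and the protocol admits limited power elsewhere. All of this stands. It makes the sentence true under conditions that the plan neither states nor quantifies.

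Three stronger readings are tempting, and the documents do not support them.
- **That the sentence is wrong for every analysis, or that any fading lowers power.** Keeping 75% of the effect still gains at correlations of 0.3 and 0.5 (74% and 65% v 63%), and so does the second both-arms relapse case at 0.3 (68%).
- **That the postpartum visits can never inform the primary contrast.** The zero gain assumes complete data. If some 28-34 week values are missing, correlated later values could contribute a little.
- **That the plan says GEE power cannot be computed.** It says only that no algorithm based on effect size exists. Even so, the stand-in was avoidable: visit-specific rates and a correlation are enough for the calculation above.

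**Conclusion.** The unconditional statement does not hold. For the primary outcome with complete data, GEE power is that of the 28-34 week comparison: about 61-63% for 50% v 30% with 60 per group, not 91%. For the averaged effect at constant control rates, added visits raise power only when the postpartum share of the effect exceeds about 0.59, 0.72 or 0.84 at correlations of 0.3, 0.5 or 0.7. Below that, the pooled test is weaker than the single visit. Even a fully sustained effect at constant rates reaches 91% only at a correlation of about 0.2 or less; under the both-arms relapse case with the gap held, it does so at about 0.3.

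The persistence shares, correlations and two-sided test are assumptions, since the documents give none of them. Clustering with one clinic per arm is ignored throughout. If the baseline visit, when all participants are tobacco users, were also averaged in, the effect would be diluted further. The point concerns a stated power property. It leaves the design, the data and the choice of GEE as they are.

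**What to change.** Delete the sentence saying that GEE power will be no lower, and the reliance on there being no GEE power algorithm. Write instead: *Power for the primary outcome is that of the 28-34 week two-group comparison, about 61-63% for 50% v 30% with 60 per group; with complete data the postpartum visits do not increase it.* The number belongs in that sentence; without it, 91% would still be read as the power for the primary outcome.

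If a pooled GEE figure is kept, state the target contrast and the visits that enter it, with the assumed postpartum rates in each arm, within-woman correlation and dropout. Give power as a range over those values.

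The cost is a few SAP sentences and a less favourable stated figure. Nothing changes for participants or data collection.
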